### **5.4. Specific Restrictions/Requirements**

All patients must be available at the study center for approximately 8 hours on Day 1 of Cycle 1 for administration of the first dose of AK-01, PK sampling, and safety assessments. Patients must also be available at the study center for approximately 8 hours after the first dose on Day 15 of Cycle 1 in order to perform PK sampling and safety assessments.

Tumor biopsy will involve observation for safety monitoring according to the institutional standard of care (typically 4-6 hours).

Periodic visits to the study center will also be necessary as described in the schedule of events (Appendix 1).

### **5.5. Blinding**

This will be an open-label study.

## 5.6. Concomitant Therapy

All concomitant medication administered from the time of first dose until the last dose of IMP must be recorded, along with the reason for use and date of administration. This includes over-the-counter or prescribed medications, vitamins and herbal supplements.

All concomitant medication administered to treat an ongoing AE or serious adverse event (SAE) must be recorded until the events resolve, the events are no longer considered to be drug-related, the patient dies or is lost to follow-up, or a new treatment is initiated for the patient.

While on study, patients may be administered medications at the discretion of the investigator to treat AEs or as supportive care (e.g., anti-emetics, antibiotics, etc.).

BC patients on a stable regimen of bone health agents (e.g., selective estrogen receptor modulators, bisphosphonates, etc.) may continue treatment.

Hematopoietic growth factors (e.g., erythropoietin, G-CSF) may be administered in this study according to institutional guidelines except in Cycle 1 of Phase I. Hematopoietic growth factors will be allowed in Cycle 1 of Phase I if a patient experiences neutropenia that is declared a DLT.

Blood product transfusions will be permitted throughout the study

CCI

CCI

Other chemotherapy, investigational therapy, molecularly-targeted therapy and cancer-related hormone therapy will be prohibited within 14 days prior to study enrollment (6 weeks for mitomycin-C or nitrosoureas) and throughout the study. Biologic therapy and immunotherapy will be prohibited within 21 days prior to study enrollment and throughout the study.

Radiotherapy to non-target lesions will be permitted on study if approved by the sponsor.

Anticoagulants (e.g., oral anticoagulants, low molecular weight heparin), antiplatelets (e.g., acetylsalicylic acid, P2Y12 inhibitors), and nonsteroidal anti-inflammatory drugs (e.g., ibuprofen, naproxen) should be stopped prior to tumor biopsy according to institutional practice.

Any patient with questions regarding concomitant therapies will be asked to contact the investigator.

## 6. PHARMACOKINETIC, PHARMACODYNAMIC, SAFETY AND EFFICACY DATA COLLECTION

All supplies for collection and shipment of blood and tissue samples for PK, PD, and molecular profiling will be provided. Further instructions will be provided on sample collection, processing, storage, and access.

### 6.1. Pharmacokinetic Evaluations

#### 6.1.1. Samples for Pharmacokinetic Evaluations

At the visits and times specified in the schedule of events (Appendix 1), venous blood samples of approximately 3 mL will be collected from all patients to determine the plasma concentrations of AK-01. The actual date and time (24-hour clock time) of each sampling will be recorded. Pre-dose samples should be obtained no more than 1 hour prior to dosing. The sampling schedule may be modified following review of PK data from the first cohort in Phase I to optimize collection times.

A maximum of 3 additional PK samples may be drawn at other time points during the study, if warranted and agreed upon by both the investigator and the sponsor.

#### 6.1.2. Bioassay

Samples for AK-01 concentration will be analyzed using a validated tandem liquid-chromatography/mass spectrometry method at a laboratory designated by the sponsor.

### 6.2. Pharmacodynamic Evaluations

#### 6.2.1. Samples for Pharmacodynamic Evaluations

Hematology samples (see Appendix\_1) will be used to evaluate a variety of hematological parameters, including white blood cell count, neutrophil count, and lymphocyte count. Changes in hematological parameters may be compared across time points and to AK-01 PK.

In Phase I, pre-treatment and on-treatment skin biopsies will be mandatory for all patients (see Appendix 1). For all Phase I patients enrolled in the P2D confirmation cohorts (after identification of the MTD, see [Section 3.1.3](#)), pre-treatment and on-treatment biopsies of primary or metastatic tumor will also be required (see Appendix 1). For all patients enrolled in Phase II, tumor biopsies will be required from either a primary or metastatic tumor site. SCLC patients tumor biopsies will be required unless the primary or metastatic tumor site is inaccessible or a quality biopsy cannot be obtained. The initial tumor biopsy should be collected after the patients previously failed therapy and prior to C1D1, and the second biopsy should be collected at C2D8,  $\pm$  3 days. Archived specimen(s) from a diagnostic biopsy and/or surgery of the tumor may be requested instead of pre-treatment tumor biopsy as long as the biopsy was obtained after they had already failed previously therapy. Tumor samples may be used for both PD and molecular profile analyses (see [Section 6.3](#)).

### *6.2.2. Evaluation of Target Engagement*

Markers of dose-dependent target engagement will be evaluated, which may include assessment of levels of phospho-histone H3 and markers of apoptosis, phosphorylation, DNA damage, and mitosis. Samples may be assessed using immunohistochemistry, Western blotting, ELISA, or other techniques, and will be compared across time points. The inhibition of AurA and AurB by AK-01 will be compared. Markers of dose-dependent target engagement may be compared between skin (collected in phase I) and tumor tissue.

## **6.3. Molecular Profile Evaluation**

### *6.3.1. Samples for Molecular Profile Evaluations*

A pre-treatment tumor biopsy is required for all patients in Phase II for assessment of molecular profile (SCLC tumor/metastatic site biopsies are collected if possible). If available, archived sample(s) from a diagnostic biopsy/surgery of the primary or metastatic tumor collected prior to enrollment may be requested instead as long as the biopsy was obtained after they had already failed previously therapy. Any other tumor samples collected in the course of the study may also be profiled (see [Section 6.2.1](#)).

Blood samples for molecular profiling will be collected on Day 1 of every cycle and at discontinuation.

### *6.3.2. Evaluation of Molecular Profile*

DNA and/or proteins from tumor samples and blood may be analyzed using immunohistochemistry staining, next generation sequencing or other technology to identify the presence of certain proteins or DNA mutations (e.g., Rb, PTEN, myc, and TP53). Somatic mutations may be identified through analysis of paired data from tumor tissue and blood, if data is not already available in patient histories. These samples may be used to evaluate the genetic mechanisms underlying response to AK-01.

Measures of efficacy may be compared between patients with different molecular tumor profiles.

## **6.4. Storage of Samples**

Biological samples collected for analysis of PD or molecular profile (i.e., blood, serum, plasma, skin (phase I only), and tumor tissue) will be retained for a maximum of 15 years following the last patient visit.

Samples collected for specified laboratory tests will be destroyed within 60 days of receipt of confirmed test results. When scientific circumstances warrant, it is acceptable to retain samples until the end of the study to confirm the validity of the results. Certain samples may be retained for a longer period if necessary to comply with applicable laws, regulations, or laboratory certification standards.

Bioanalytical samples collected to measure AK-01 concentration will be retained for a maximum of 1 year following last patient visit for the study (unless local/national regulations stipulate longer). During this time, samples remaining after bioanalysis may be used for other described analyses.

## 6.5. Safety Evaluations

### 6.5.1. Safety Measures

This study contains detailed safety monitoring that will permit characterization of the safety profile of AK-01 in patients with locally advanced or metastatic tumors. See Appendix 1 for the schedule of safety assessments.

### 6.5.2. Safety Data Collection and Review

The investigator is responsible for the safety of all patients registered in this clinical study.

For all scheduled and unscheduled safety assessments, the results and investigator's assessment of clinical significance will be recorded (i.e., clinical laboratory evaluations [hematology, clinical chemistry, endocrinology, and urinalysis], ECOG status, electrocardiogram [ECG], vital signs, and physical exam).

All ECGs will be 12-lead triplicate assessments obtained using digital equipment approximately 5 minutes apart at the time points indicated in Appendix 1. CCI

Additional ECGs may be obtained if medically warranted. When an ECG is scheduled on the same day as a blood collection, the ECG will be obtained prior to blood collection. Any clinically significant ECG result will be documented as an AE. The investigator may conduct an echocardiogram (ECHO) evaluation if clinically indicated.

Clinical laboratory tests are listed in Appendix 2. For all clinical laboratory safety tests, a certified local laboratory will be used to perform laboratory analyses to guide treatment decisions and data analysis. Qualified medical staff will review, initial and date all laboratory results.

More advanced ophthalmologic exams may be done at the request of the investigator if needed.

An AE will be recorded for the result of any safety assessment (e.g., ECG, vital signs, clinical chemistry value, etc.) that requires a patient to be discontinued from the study or receive treatment. The medical condition caused by the abnormal result should be recorded, rather than the abnormal result (e.g., hyperglycemia instead of elevated glucose). For the result of any

safety assessment which requires a patient to be discontinued or receive treatment, the investigator will follow the AE to a satisfactory clinical resolution.

### 6.5.3. Adverse Events

The sponsor has standards for reporting AEs that are to be followed regardless of applicable regulatory requirements that may be less stringent. A clinical trial AE is any untoward medical event associated with the use of a drug in humans, whether or not it is considered related to that drug. Lack of drug effect is not an AE in clinical trials, because the purpose of the clinical trial is to establish drug effect.

The investigator, medical monitor, and sponsor will review the collected data regularly for evidence of AEs. All patients will be assessed routinely for AEs as outlined in the schedule of events (Appendix 1). All AEs must be reported to the sponsor or its designee regardless of relatedness to IMP or protocol procedures from the time the patient signs the informed consent documents (ICD) to when the patient receives the last dose of IMP. Thereafter, AEs will only be reported if ongoing or considered related (possibly or probably) to the IMP.

The investigator will notify the sponsor or designee prior to reducing a patient's dose or discontinuing treatment. If a patient's dose is reduced or treatment is discontinued as the result of an AE, study personnel will clearly document the circumstances and data leading to dose reduction/treatment discontinuation.

While the patient is on study, study personnel will record any change in medical history or preexisting condition(s). Events leading to the clinical outcome of death due to progression will be included as part of the safety and efficacy analyses for this study, but will not require immediate reporting to the sponsor or its designee as AEs, unless the investigator believes the event may have been caused by the IMP. Signs and symptoms of progression of the disease under study will not be considered AEs in this study.

Cases of pregnancy that occur during maternal or paternal exposures to IMP will be reported. Data on fetal outcome and breast-feeding are collected for regulatory reporting and drug safety evaluation. Upon documentation of pregnancy, the patient must be removed from the study, and treatment with IMP must be stopped immediately.

The investigator will decide whether he or she interprets the observed safety signals as related to the IMP. To assess the relationship of the AE to administration of AK-01, the following terminologies are defined:

- **Probably related:** a direct cause and effect relationship between the IMP and the AE is likely.
- **Possibly related:** a cause and effect relationship between the IMP and the AE has not been demonstrated at this time and is not probable, but is also not impossible.
- **Unlikely:** likely to be due to another etiology.
- **Not related:** without question, the AE is definitely not associated with the IMP.

The severity of all AEs will be graded using CTCAE version 4.03. [Table 4](#) presents general guidelines for evaluating severity by CTCAE; see Appendix 9 for severity guidelines by AE.

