not be reported as SAEs, however if an AE occurs during hospitalization for preplanned surgery that meets the above criteria, it will be reported as an SAE. SAEs due to progressive disease (including death) should not be reported as SAEs unless the investigator also deems there is a possible contribution of the IMP.

All SAEs occurring from the time the patient signs the ICD until the 30-day Follow-up visit must be reported to the sponsor or its designee regardless of relatedness to IMP or protocol procedures. Thereafter, SAEs will be reported only if the investigator feels the events were related to the IMP or a protocol procedure. Any SAEs after ICD signature and prior to administration of IMP will be reported if the investigator feels the events were related to a protocol procedure.

Appendix 1 outlines specific safety assessments for the 30-day Follow-up visit. All drug-related AE and SAEs will be followed until the events resolve, the events are no longer considered to be drug-related, the patient dies or is lost to follow-up, or until a new treatment is initiated for the patient. Frequency of follow-up evaluation is left to the discretion of the investigator.

The medical representative of the sponsor will monitor safety data throughout the course of the study. The sponsor and/or its designee will review SAEs within appropriate timeframes to meet reporting obligations imposed by regulatory authorities. All serious and unexpected AEs for this study will be reported to regulatory authorities in accordance with local laws, directives and regulations.

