- v. Patients will attend a follow-up visit 30 days (+/- 7 days) following the last dose of IMP.
- w. Patient survival will be confirmed approximately every 3 months for up to 1 year.

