## 7.3. General Definitions

**Treatment start date** is defined as the first date when a nonzero dose of AK-01 was administered. It will be derived based on the “AK-01 compliance” eCRF page.

**Treatment end date** is defined as the last date when a nonzero dose of AK-01 was administered. It will be taken from the field “Date of last drug intake” in the “Discontinuation from study treatment” eCRF page.

**Study day** for all assessments will be derived from the Treatment start date. It will be calculated as follows:

- Date of assessment – Treatment start date + 1; for assessments on or after Treatment start date
- Date of assessment – Treatment start date; for assessments before Treatment start date

**Last contact date** will be derived as the latest date of the following:

- Date of any visit
- Date of any other assessment, i.e. date of ECG, ECOG assessment, physical examination or pregnancy test, Date of blood sampling (laboratory tests, molecular profile, PK), date of skin/tumor biopsy, Date of last drug intake, date of discontinuation, start/end date regarding AK-01 compliance, AEs or concomitant medications, date of assessment regarding the response evaluation
- Date of last known alive in the Survival eCRF page

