## **9.8. Analyses of Safety**

Unless specified otherwise, all safety analyses will be performed in the FAS. Only safety assessments collected no later than 30 days after the Treatment end date will be summarized in tables. All safety assessments entered in the eCRF

(scheduled and unscheduled) will be listed and the assessments that did not occur within this timeframe will be flagged.

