### 9.8.2. Adverse Events

Detailed definitions and classification of AEs are specified in the Protocol, Section 6.5.3. All AEs will be coded using the MedDRA version 20.0 terminology and graded using NCI CTCAE v. 4.03.

A treatment-emergent AE is an AE that started or worsened (i.e. increased in severity) from the Treatment start date to 30 days after the Treatment end date. Only treatment-emergent AEs will be summarized in the tables. All AEs entered in the eCRF will be listed and AEs not considered as treatment-emergent will be flagged.

The data will be presented by cohort, see Section 7.6 regarding an assignment of particular AEs to the cohorts.

The number and frequency of patients reporting each treatment-emergent AE will be summarized by primary System Organ Class (SOC) and Preferred Term (PT), where subjects with more than one AE within a particular SOC and PT are counted only once for that SOC and PT.

To assess the relationship of the AE to administration of AK-01, the following terminologies are defined by the protocol: probably related, possibly related, unlikely, not related. For tables summarizing AEs related to AK-01, the options probably related and possibly related will be considered.

The following AE summaries will be presented (sorted alphabetically unless specified otherwise):

- Treatment-emergent adverse events, by SOC and PT
- Treatment-emergent adverse events in Cycle 1, by SOC and PT
- Treatment-emergent adverse events related to AK-01, by SOC and PT
- Treatment-emergent adverse events, by PT (sorted by overall decreasing frequency)
- Treatment-emergent adverse events in Cycle 1, by PT (sorted by overall decreasing frequency)
- Treatment-emergent adverse events related to AK-01, by PT (sorted by decreasing frequency)
- Treatment-emergent adverse events, by PT and maximum CTCAE grade (sorted by overall decreasing frequency)
- Treatment-emergent adverse events related to AK-01, by PT and maximum CTCAE grade (sorted by overall decreasing frequency)

- Treatment-emergent adverse events leading to dose reductions or interruptions, by SOC and PT
- Treatment-emergent adverse events related to AK-01 leading to dose reductions or interruptions, by SOC and PT
- Discontinuations due to adverse event, by SOC and PT
  - These events will be identified as AEs that have “Action taken with study drug” reported as “Drug withdrawn” AND at the same time, in the “Discontinuation page”, the reported reason is “Unacceptable toxicity”.

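### All-cause TEAE tables run 30 days past the last dose, but new non-serious AEs judged unrelated are no longer collected in that period

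*Protocol*

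**What the plan says.** **Collection.** Protocol 6.5.3 requires AEs of any causality from consent "to when the patient receives the last dose of IMP". From then on the rule narrows: "Thereafter, AEs will only be reported if ongoing or considered related (possibly or probably) to the IMP". Serious events follow a longer rule in Protocol 6.5.4: "All SAEs occurring from the time the patient signs the ICD until the 30-day Follow-up visit must be reported", whatever their cause. The timing of that visit comes from footnote v of the schedule of events in Protocol Appendix 1: "Patients will attend a follow-up visit 30 days (+/- 7 days) following the last dose of IMP".

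**Reporting.** SAP 9.8.2 counts an AE as treatment-emergent if it started or worsened "from the Treatment start date to 30 days after the Treatment end date". It adds: "Only treatment-emergent AEs will be summarized in the tables". The summaries by SOC and PT, by PT, and by PT and maximum grade, and the any-TEAE line of the overall summary, have no causality restriction; separate tables are restricted to related events. SAP 9.8 applies the same cut-off to safety data in general: "Only safety assessments collected no later than 30 days after the Treatment end date will be summarized in tables". SAP 7.3 defines the Treatment end date as "the last date when a nonzero dose of AK-01 was administered".

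SAP section 2, which lists changes from the protocol, mentions only the type of biopsy in a Phase I exploratory objective.

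**The concern.** The reporting window is longer than the window in which the data feeding it are required. After the last dose, whether a new non-serious AE reaches the database depends largely on a causality judgement made by an investigator who knows the treatment. A table headed as all-cause would then mix full collection on treatment with selective collection afterwards, without telling the reader.

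Safety and tolerability is a secondary objective in both phases. With no control arm, the absolute incidence is itself the safety result; there is no comparison in which an equal shortfall could cancel. All-cause incidence could be too low, and related events could look like a larger part of the total after the last dose than they are.

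The SAP handles another data stream consistently. Protocol 5.6 records concomitant medication to the last dose (longer if it treats an ongoing AE), and SAP 9.7.2 summarizes only medication used during treatment. AEs were not aligned in this way.

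**Working it through.** The documents state no figure to reproduce, so the check sets the rules side by side and then does a short calculation.

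**Step 1: common anchor.** The protocol's narrowing point is the last dose. The SAP's Treatment end date is the last nonzero dose. Both windows start from the same day and differ by 30 days.

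**Step 2: what is still collected in those 30 days.**

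| Event after the last dose | Required? | Source |
|---|---|---|
| New, non-serious, possibly or probably related | Yes | Protocol 6.5.3 |
| Ongoing at last dose, any cause, including worsening | Yes | Protocol 6.5.3; worsening counts under SAP 9.8.2 |
| Serious, any cause | Yes, to the 30-day visit | Protocol 6.5.4 |
| Clinically significant examination or vital-sign finding | Recorded as an AE, no causality limit | Protocol Appendix 1, footnotes j and k |
| Clinically significant ECG result, or safety finding that needs treatment | Recorded as an AE, no causality limit | Protocol 6.5.2 |
| Other new, non-serious, unlikely or not related | No | Protocol 6.5.3 |

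The gap is the last row.

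**Step 3: share of window time.** Cycles last 21 days (Protocol 5.2.2). Tail share = 30 / (21 × cycles + 30).

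- 1 cycle: 30/51 = 58.8%
- 2 cycles: 30/72 = 41.7%
- 4 cycles: 30/114 = 26.3%
- 8 cycles: 30/198 = 15.2%

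**Step 4: illustration under an assumed rate.** The documents give no AE rates. Assume a constant rate r per 30 days of a first unrelated non-serious AE, so λ = r/30 per day; a cohort of 30 patients, all treated for T days; and no tail event captured by any other route. Expected missed patients = 30 × [exp(−λT) − exp(−λ(T + 30))].

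For 2 cycles (T = 42):

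- r = 0.05: 30 × [exp(−0.07) − exp(−0.12)] = 1.4
- r = 0.20: 30 × [exp(−0.28) − exp(−0.48)] = 4.1

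Over the same range of r, the result is 1.4 to 4.7 patients for 1 cycle, 1.3 to 3.1 for 4 cycles and 1.1 to 1.8 for 8 cycles. For the assumed rates these are upper limits, because Step 2 shows other routes of entry. They are not estimates for this trial.

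**Step 5: SAEs.** The 30-day visit may fall from day 23 to day 37, and Protocol 4.2.1 allows the follow-up assessments sooner if new anti-cancer treatment starts. With a day-23 visit, required collection of unrelated SAEs ends 30 − 23 = 7 days before the SAP window closes.

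**The case against.** The strongest case on the other side is that little is lost.

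- Protocol 6.5.3 defines possibly related so broadly that only events with another likely cause, or clearly unconnected to the drug, drop out.
- Unknown causality is handled as related (Protocol 8.2, SAP 9.1.3), and signs and symptoms of progression are not AEs at all (Protocol 6.5.3).
- AE monitoring is scheduled at the Discontinuation and 30-day visits, so some unrelated events will be entered anyway.
- A patient counts once per SOC and PT, so a tail event adds nothing if that patient already had the same PT on treatment.
- The tables are descriptive, no decision rule uses them, and the SAP plans no statistic for the related share.

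All of this stands, and it limits the size of the problem. It does not close the gap. The additional routes make capture depend on the type of event and on which protocol text a site follows, so the tail is still not all-cause.

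Two stronger readings are tempting. A reader might infer that the tail holds nothing but related events and SAEs. The documents do not support that: ongoing AEs stay reportable whatever their cause, and several kinds of finding are recorded without a causality limit. A reader might also take 42% or 15% as the share of AEs missed. Those are shares of calendar time; without AE rates they say nothing about events or patients.

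**Conclusion.** The mismatch is real and the SAP does not acknowledge it. If both documents are followed exactly, the all-cause TEAE tables (SOC and PT, PT, maximum grade, and the any-TEAE line) are selectively incomplete for the 30 days after the last dose. Incidence may be understated; the direction is clear, but the size cannot be derived from the documents. The counts in Step 4 rest wholly on the assumed rate of 5% to 20% per 30 days and on no other capture.

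Essentially unaffected are:

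- the related-AE tables, because related events remain reportable;
- dose-limiting toxicities, which by definition are related events in Cycle 1;
- the Cycle 1 tables, except for patients who stop during Cycle 1;
- the test of the objective response rate.

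All-cause SAE tables are affected only in the last days of the window, when the follow-up visit is early. The point concerns the accuracy of secondary safety reporting. It does not threaten the primary analyses, but should be settled before database lock.

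**What to change.** **In the SAP (sufficient alone, and applicable to all patients).** End the all-cause non-serious TEAE tables, and the any-TEAE line, at the Treatment end date. Show related AEs, and all SAEs, to day 30 in separate tables. Footnote every table with its window and with what was collected after the last dose. The SAE footnote should add that collection regardless of cause ends at the follow-up visit, which may precede day 30. The footnotes matter because a patient whose only AE is a related one after the last dose would appear in the related table and not in the all-cause table; counts with different windows must not be compared directly. Record the difference in SAP section 2.

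**Alternatively, for patients still to be followed.** Amend Protocol 6.5.3 to collect all AEs regardless of relatedness through 30 days after the last dose, and end the SAP window at the earlier of day 30 and the actual follow-up visit. Tying collection to the visit while keeping a fixed 30-day reporting window would leave a gap whenever the visit is early.

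**Cost.** The SAP route costs a few sentences and footnotes, and a shorter all-cause window that drops some tail events that were collected. The protocol route adds a few AE records at a visit that already takes place, but needs sponsor and IEC/IRB approval (Protocol 9.4). It cannot recover data for patients already past follow-up: dosing began in June 2017 and SAP version 2.0 is dated 31 January 2019. Those patients stay under the old rule, so the tables would need to show which collection rule applied to whom.
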